5.2.3 Phase 2a Inclusion Criteria

A subject will be eligible for study participation if he/she meets the following criteria:

1. The subject must be ≥ 18 years of age.
2. The subject must have CLL and require treatment in the opinion of the investigator.
3. The subject has relapsed disease and has received no more than 5 prior myelosuppressive/chemotherapy regimens.
4. Subject has an Eastern Cooperative Oncology Group performance score of ≤ 1 .
5. Subjects receiving Selective Serotonin Reuptake Inhibitor (SSRI) anti-depressants (e.g., Prozac) must be receiving a stable dose for at least 21 days prior to the first dose of study drug.

6. The subject must have adequate bone marrow independent of growth factor support (with the exception of subjects with ANC < 1000/ μ L and bone marrow heavily infiltrated with underlying disease [80% or more]), renal and hepatic function, per local laboratory reference range at Screening as follows:
 - Bone marrow: Absolute Neutrophil count (ANC) \geq 1000/ μ L; Platelets \geq 75,000/ mm^3 (entry platelet count must be independent of transfusion within 14 days of Screening); Hemoglobin \geq 9.0 g/dL;
 - Renal function: Serum creatinine \leq 2.0 mg/dL or calculated creatinine clearance \geq 50 mL/min;
 - Hepatic function and enzymes: AST and ALT \leq 3.0 \times the upper normal limit (ULN) of institution's normal range; Bilirubin \leq 1.5 \times ULN. Subjects with Gilbert's Syndrome may have a Bilirubin > 1.5 \times ULN;
 - Coagulation: aPTT, PT must not exceed 1.2 \times ULN.
7. Female subjects must be surgically sterile, postmenopausal (for at least 1 year), or have negative results for a pregnancy test performed as follows:
 - At Screening on a serum sample obtained within 14 days prior to initial study drug administration, and
 - Prior to dosing on a urine sample obtained on Lead-in Day 1 if it has been > 7 days since obtaining the serum pregnancy test results.
8. All female subjects not surgically sterile or postmenopausal (for at least 1 year) and non-vasectomized male subjects must practice at least one of the following methods of birth control:
 - total abstinence from sexual intercourse (minimum one complete menstrual cycle);
 - a vasectomized partner;
 - hormonal contraceptives (oral, parenteral or transdermal) for at least 3 months prior to study drug administration;
 - double-barrier method (including condoms, contraceptive sponge, diaphragm or vaginal ring with spermicidal jellies or cream).

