 - j. The specific laboratory tests required for chemistry, hematology and urinalysis are listed in [Table 7](#). Triglycerides will only be collected at Screening and at the Final Visit. Amylase and lipase will be collected at Screening, Cycle 1 Day 15, and Final Visit. For any subjects who are at high risk for tumor lysis syndrome (TLS) during Cycle 2 and beyond, additional samples for hematology and chemistry may be collected as per the management guidelines in Section [6.7.4](#).
 - k. Assessment for tumor response will be performed at the end of Cycle 2, end of Cycle 4, end of every 4 cycles through Cycle 20 (i.e., C8, C12, C16, C20), end of every 8 cycles thereafter (i.e., C28, C36, C44. . .) and at the Final Visit. Analysis of peripheral blood for tumor response will be performed on Day 1 (pre-dose) of the following cycle for every tumor assessment.
 - l. A CT scan will be performed at Screening (within 21 days prior to study drug administration).
 - m. Assessments for tumor response will be repeated 2 months after NCI-WG (1996) criteria for a complete remission (CR) are first met and/or at least 2 months after IWCLL updated NCI-WG (2008) criteria for a complete remission (CR or CRi) or partial remission (PR) are first met.
 - n. If clinical and laboratory criteria for a CR or PR are met), a bone marrow aspirate/biopsy and CT scan should be performed at least 2 months after the criteria are first met in order to confirm a CR or PR. A bone marrow aspirate/biopsy will be performed at the end of Cycle 8 (for all subjects regardless of response) if the subject is continuing to receive ABT-263.
 - o. Bone marrow aspirate/biopsy will be done at Screening (within 21 days prior to study drug administration) unless a bone marrow aspirate and biopsy was obtained within 12 weeks of starting study drug without intervening treatment and is representative of the subject's existing disease.
 - p. Serious adverse event assessment will be performed at Screening after informed consent has been obtained.
 - q. Adverse events will be followed until satisfactory clinical resolution of the adverse event is achieved.
 - r. Survival assessments will be collected every 3 months for 2 years following discontinuation from the study (including the extension portion of the study). In Protocol Amendment #12 this information will no longer be collected.

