A CT scan of involved anatomic regions (or MRI, if medically indicated) will be done at Screening (within 21 days prior to the first dose of study drug). CT scans and MRIs performed as standard of care throughout the study should also be captured on a case report form.

Phase 1

If a subject meets all the clinical and laboratory criteria for a complete remission (CR) or a partial remission (PR), a CT scan should be performed at least 2 months after the criteria are first met in order to confirm a CR or PR.

Phase 2a

If a subject meets all the clinical and laboratory criteria for a complete remission (CR) or a partial remission (PR), a CT scan should be performed at least 2 months after the criteria are first met in order to confirm a CR or PR.

Tumor Assessments

Analysis of peripheral blood, physical examination, bone marrow aspirate and biopsy, CT scan of involved anatomic regions and MRI (if medically indicated), will be utilized for disease assessment as described above.

Phase 1

Subjects will be evaluated against the IWCLL updated NCI-WG (January 2008) criteria³¹ (physical examination/CT/MRI) at the end of Cycle 2, the end of Cycle 4, end of every 4 cycles through Cycle 20 (i.e., C8, C12, C16, C20), end of every 8 cycles thereafter (i.e., C28, C36, C44. . .) and at the Final Visit. For the Extension Study, subjects will be evaluated against the IWCLL updated NCI-WG (January 2008) criteria (physical

examination/CT/MRI) at the Final Visit. Analysis of peripheral blood will be evaluated against the NCI-WG criteria for tumor response assessment on Day 1 (pre-dose) of the following cycle for every tumor assessment. For example, when a subject completes Cycle 2, the laboratory values from Day 1 of Cycle 3 (pre-dose) will be used to assess tumor response.

The tumor assessment performed at Screening will serve as the baseline for clinical assessment. Assessments for tumor response will be repeated at least 2 months after NCI-WG criteria for complete remission (CR or CRi) are first met. Assessments for tumor response will be repeated at least 2 months after criteria for a partial remission (PR) are first met. Response criteria will be assessed while subjects continue treatment with ABT-263. Response criteria definitions are outlined in Section 5.3.3.1.

Phase 2a

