3. No hepatomegaly or splenomegaly by physical examination. A CT scan of the abdomen should be performed at response assessment if found to be abnormal prior to the start of study drug or if physical exam is inconclusive at the time of evaluation.
4. Absence of constitutional symptoms.
5. Normal CBC as exhibited by:
 - Polymorphonuclear leukocytes $\geq 1,500/\mu\text{L}$ without G-CSF support.
 - Platelets $> 100,000/\mu\text{L}$.
 - Hemoglobin $> 11.0 \text{ g/dL}$ (untransfused or without erythropoietin support).

Bone marrow aspirate and biopsy should be performed at least 2 months after clinical and laboratory results demonstrate that all of the requirements above have been met to demonstrate that a CR has been achieved. The marrow should be analyzed by flow cytometry and/or immunochemistry to demonstrate that the marrow is free of clonal B-CLL cells. Note: cases with residual CLL cells by conventional flow cytometry or immunohistochemistry are defined as a PR.

Subjects who fulfill all the criteria for a CR, but who have persistent anemia, thrombocytopenia or neutropenia apparently unrelated to CLL, but related to drug toxicity should be considered as a different category of remission, CR with incomplete bone

marrow recovery (CRi). The marrow evaluation should be performed with scrutiny and not show any clonal infiltrate. Subjects should be monitored prospectively to determine whether or not their outcome differs from that of patients with detectable residual disease or with non-cytopenic PR.

Partial Remission (PR) requires at least two of the following for a period of at least 2 months:

1. $\geq 50\%$ decrease in peripheral blood lymphocyte count from the pretreatment baseline value.
2. $\geq 50\%$ reduction in lymphadenopathy (assessed by CT scan):
 - In the sum of products of up to 6 lymph nodes, or
 - In one lymph node diameter if only a single lymph node was present at baseline.
3. No increase in any lymph node, and no new enlarged lymph node. In small lymph nodes (< 2 cm), an increase of $< 25\%$ is not considered to be significant.
4. $\geq 50\%$ reduction in the size of the liver and/or spleen (if abnormal prior to therapy) as defined by CT scan.

In addition **one or more** of the following criteria must be met:

- Polymorphonuclear leukocytes $\geq 1,500/\mu\text{L}$ or 50% improvement over baseline without G-CSF support.
- Platelets $> 100,000/\mu\text{L}$ or 50% improvement over baseline.

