- Hemoglobin > 11.0 g/dL or 50% improvement over baseline without transfusions or erythropoietin support.

Progressive Disease (PD) requires at least one of the following:

1. Appearance of any new lesions such as enlarged lymph nodes (> 1.5 cm), splenomegaly, hepatomegaly or other organ infiltrates.

2. $\geq 50\%$ increase in the sum of the products of diameters of multiple nodes
3. $\geq 50\%$ in the greatest determined diameter of any previous site. A lymph node of 1-1.5 cm must increase by $\geq 50\%$ to a size greater than 1.5 cm in the longest axis. A lymph node of more than 1.5 cm must increase to more than 2.0 cm in the longest axis.
4. $\geq 50\%$ increase in the size of the liver and/or spleen or the de novo appearance of hepatomegaly or splenomegaly.
5. $\geq 50\%$ increase in the absolute number of blood lymphocytes with at least 5,000 B-lymphocytes per μL .
6. Transformation to a more aggressive histology (e.g., Richter's syndrome or PLL with $> 55\%$ prolymphocytes).
7. Occurrence of cytopenia (neutropenia, anemia or thrombocytopenia) attributable to CLL.
 - The progression of any cytopenia (unrelated to autoimmune cytopenia), as documented by a decrease of Hb levels by more than 2 g/dL or to less than 10 g/dL, or by a decrease of platelet counts by more than 50% or to less than 100,000/ μL , defines disease progression, if the marrow biopsy demonstrates an infiltrate of clonal CLL cells.

Subjects who have not achieved a CR or a PR, or who have not exhibited PD will be considered to have Stable Disease (SD).

A summary of the criteria described above is included in [Table 11](#).

Table 11. IWCLL Updated NCI-WG Criteria for Tumor Response (2008)

Criteria	Complete Remission (CR)	Partial Remission (PR)	Progressive Disease (PD)	Stable Disease (SD)
Lymphadenopathy	None above 1.5 cm	≥ 50% reduction	≥ 50% increase	Change of -49% to +49%
Hepatomegaly and/or Splenomegaly	Absent	≥ 50% reduction	≥ 50% increase or new hepatomegaly and/or splenomegaly	Change of -49% to +49%
Constitutional Symptoms	Absent	Present	Present	Present
Polymorphonuclear Leukocytes	≥ 1500/μL	≥ 1500/μL or > 50% improvement over baseline without G-CSF support	Not specified	Not specified
Circulating clonal B-lymphocytes	None	≥ 50% reduction from baseline	≥ 50% increase over baseline	Change of -49% to +49%
Platelets	> 100,000/μL	> 100,000/μL or ≥ 50% improvement from baseline	Decrease of ≥ 50% from baseline secondary to CLL	Change of -49% to +49%

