5.4 Removal of Subjects from Therapy or Assessment

5.4.1 Discontinuation of Individual Subjects

Each subject has the right to withdraw from the study at any time. In addition, the investigator will discontinue a subject from the study at any time if the investigator considers it necessary for any reason including:

- The investigator believes it is in the best interest of the subject.
- The subject's response to therapy is unsatisfactory, as evidenced by progression of disease.
- The subject experiences toxicities that require more than a 3-week dose interruption.
- The subject requires more than two dose reductions, in the absence of objective response to ABT-263.
- The subject requires radiotherapy, cancer-related surgery, or alternate anti-neoplastic agents during the study period.
- The subject becomes pregnant or begins breastfeeding.
- The occurrence of an adverse event that precludes further investigational drug administration.
- Noncompliance with the protocol.
- The subject requires anti-coagulant or anti-platelet therapy during the study period.

In addition, subjects in the Extension Study may also be discontinued for following reasons:

- The Extension Study has been ongoing for 11 years since the transition of the last subject into the Extension Study.
- ABT-263 becomes commercially available.

- AbbVie no longer pursues ABT-263 in this indication.

The investigator will inform AbbVie prior to discontinuing a subject from the study by contacting the Clinical Team Leader as identified in Section 7.0.

During the COVID-19 pandemic, it has been necessary to employ mitigation strategies to enable the investigator to ensure subject safety and continuity of care.

The investigator should contact the sponsor medical contact before discontinuing a subject from the study for a reason other than "planned per protocol," to ensure all acceptable mitigation steps have been explored.

All subjects will be included for analysis of safety data. Subjects in the Phase 1 portion of the study who withdraw from the study will not be replaced unless they are not evaluable. Evaluable subjects are defined as those subjects who:

- Experience a DLT
- Complete at least 80% of dosing in the first cycle (of either 14/21 or 21/21 day dosing schedule)

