8.1.3.7 Reporting of Results

All subjects enrolled will be assessed for response to treatment based on the NCI-WG criteria in Section 5.3.3.1. Each subject will be assigned to one of the following categories: 1) complete remission, 2) complete remission with incomplete bone marrow recovery, 3) partial remission, 4) stable disease, 5) progressive disease, 6) early death from malignant disease, 7) early death from toxicity, 8) early death because of other cause, or 9) unknown (not assessable, insufficient data).

Subjects in response categories 5-8 will be considered as failing to respond to treatment (disease progression). Thus, an incorrect treatment schedule or drug administration will not result in exclusion from the analysis of a response.

Sub-analyses may be performed on the subset of subjects for whom major protocol deviations have not been reported (e.g., early discontinuation of treatment, major protocol violations, etc.). The reasons for excluding subjects from the analysis will be clearly reported.

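### The 2008 partial remission rule counts absence of node growth as one of its two required signs, and the reference for progression is not stated for every endpoint that uses it

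*Protocol*

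**What the plan says.** **Partial remission.** For the 2008 criteria, Protocol Section 5.3.3.1.2 states: "Partial Remission (PR) requires at least two of the following for a period of at least 2 months". Items 1, 2 and 4 are reductions of at least 50% in blood lymphocytes, in nodes by CT, and in liver or spleen by CT if abnormal before therapy. Item 3 is "No increase in any lymph node, and no new enlarged lymph node". One of three blood-count conditions must also be met; an absolute level is enough (neutrophils at least 1,500/µL, platelets above 100,000/µL, or hemoglobin above 11 g/dL).

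**Progression.** The first PD item in the same section is "Appearance of any new lesions such as enlarged lymph nodes (> 1.5 cm), splenomegaly, hepatomegaly or other organ infiltrates". Section 8.1.3.7 states: "Each subject will be assigned to one of the following categories". It does not say which category applies when PR and PD are both met.

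**Reference for progression.** Protocol Section 8.1.3.5 and the SAP (Duration of Overall Response) measure PD from the smallest measurement since treatment started. Table 11 measures PD from baseline for B-lymphocytes, platelets and hemoglobin, and names no reference for nodes or organs. PFS (Section 8.1.3.1) points to Section 5.3.3, a pointer that the SAP omits. TTP (Section 8.1.3.3) names no reference.

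**Use.** The SAP (Exploratory Efficacy) evaluates Phase 2 response on the 2008 criteria, in 31 subjects.

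**The concern.** A rule that asks for two signs of response should not let one of them be the absence of growth. As written, a subject with enlarged nodes, an enlarged spleen and lymphocytosis can be a PR on a fall in lymphocytes alone, if no node grows and one blood count is adequate, for 2 months. The blood count need not be a second sign of response. Phase 2a entry ("The subject must have adequate bone marrow independent of growth factor support") sets lower limits only: neutrophils 1,000/µL, platelets 75,000/mm³ and hemoglobin 9.0 g/dL. An adequate count can therefore already be present at Screening.

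Because item 3 is optional, its failure does not block a PR that rests on two reductions. A subject can then meet PR and PD at one assessment.

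The response rate, duration of response, PFS and TTP all depend on these definitions. If progression is measured from different references, one subject's progression date can differ between endpoints.

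**Working it through.** The plan gives no figure to reproduce: the Phase 2a size of about 32 was chosen, not calculated. The check is one of logic, followed by the scale of any effect.

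**1. Counting the PR rule.** Each of the four items is met or not met, giving 2⁴ = 16 patterns.
- At least two met: 6 + 4 + 1 = 11 patterns qualify.
- Item 3 met, with at least one reduction: 2³ − 1 = 7. Of these, 3 have exactly one reduction (lymphocytes, nodes, or liver/spleen).
- Item 3 failed, with at least two of three reductions: 3 + 1 = 4.
- Check: 7 + 4 = 11. No pattern qualifies without any reduction.
- With item 3 as a condition and two of items 1, 2 and 4 required, 4 patterns qualify. Subjects with one abnormal site need a separate provision.

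These are counts of logical patterns, not of patients.

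**2. Overlap of PR and PD.** In the 4 patterns with item 3 failed, the failure may be a new node above 1.5 cm, which is PD. Progression is a reason for discontinuation (Section 5.4.1: "response to therapy is unsatisfactory, as evidenced by progression of disease"), so the overlap arises mainly when the node is first seen at the confirming assessment. Section 5.3.1.1 places a scan there: "a CT scan should be performed at least 2 months after the criteria are first met in order to confirm a CR or PR".

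**3. Scale for the response rate.** With n = 31, each reclassified subject moves the rate by 1/31 = 3.2 points; three move it by 3/31 = 9.7 points. Exact 95% intervals for assumed counts:

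| Responders | Rate | 95% CI |
|---|---|---|
| 11/31 | 35.5% | 19.2–54.6% |
| 8/31 | 25.8% | 11.9–44.6% |

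A shift of this size is smaller than the sampling error, but the interval does not allow for a classification effect that goes one way only. The disease control rate is unchanged when a subject moves from PR to SD; it falls if precedence moves a subject from PR to PD.

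**4. Reference for progression (illustrations only).** Let B be the baseline sum of node products and r the largest fractional fall.
- From the smallest value: PD at 1.5·B·(1 − r).
- From baseline: PD at 1.5·B.
- Ratio: 1/(1 − r).
- r = 0.50: 0.75B against 1.5B, ratio 2.
- r = 0.75: 0.375B against 1.5B, ratio 4.

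These ratios apply only if PFS is derived from baseline, which no section states for nodes.

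For lymphocytes, assume 20,000/µL at baseline, all B-cells, and that smallest measurement includes counts. After a 90% fall, 1.5 × 2,000 = 3,000, so the 5,000/µL minimum applies and PD is at 5,000, against 30,000 from baseline.

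**The case against.** - **No outside standard is available.** The 2008 section is internally consistent on counting, and the guideline it cites cannot be consulted here. The 1996 rule, which requires all items, is a different set. This stands in part: the documents cannot show that the 2008 wording was miscopied. They do show that a non-response item can supply half of a PR.
- **One reduced site can be legitimate.** A subject with one abnormal site at baseline can only ever show one reduction. This stands. The fault is limited to subjects with several abnormal sites.
- **The blood-count condition is not special to 2008.** The 1996 PR has a similar one. This stands; the condition is not itself a fault.
- **Table 11 might be read as contradicting the text.** It does not, because it has no counting rule.
- **A reader might infer that four places contradict one another on the PD reference.** The documents do not support that. PFS and TTP are silent on nodes and organs. Table 11 and duration of response conflict directly only for lymphocytes, and only if smallest measurement includes counts. The Methods of Measurement text uses the word for ruler or caliper readings. For platelets and hemoglobin PD is a fall, so a smallest-value reference would make no sense.
- **Response is assessed by the investigator**, and the SAP describes no item-counting algorithm. Different dates for one subject require that two references were actually applied, which the documents do not show. PD also needs only one of seven items, so a threshold ratio is not a difference in dates. Both points weaken the concern, but investigators apply the written criteria, so they do not remove it.

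**Conclusion.** The PR wording is a real weakness in the endpoint definition. It lets a subject with several abnormal sites be a PR on one reduction, and it lets PR and PD coincide with no stated order. Any effect of the single-reduction route on the Phase 2 response rate is upward, at 3.2 points per subject. It is tempting to conclude that the reported rate is inflated. The documents do not support that, since the number affected is not given and may be zero.

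The progression reference is best described as unstated for nodes and organs in PFS and TTP, with a possible conflict for lymphocytes. It could give one subject different progression dates; the ratios of 2 and 4 are illustrations, not estimates of bias.

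Efficacy is exploratory (Section 5.3.3), there is no control group (Section 5.6.1) and response is investigator-assessed. The impact is low to moderate: it limits what the response rate, PFS, TTP and duration of response can support.

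**What to change.** For derived endpoints only, leaving treatment decisions and the criteria behind them unchanged:

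1. Re-derive Phase 2 best response where the data allow, labelled post hoc and shown beside the investigator-assessed rate. Treat item 3 as a required condition, count only items 1, 2 and 4, and keep PR reachable for subjects with one abnormal site at baseline. Let PD take precedence when both are met at the same assessment.
2. State one PD reference per variable and use it for PFS, TTP and duration of response; for example, the lowest on-study value where PD is a rise, and baseline where PD is a fall. State whether investigator-determined clinical progression (Section 5.3.3.1.3) is an event for each endpoint. It lies within the section that PFS points to, while duration of response requires objective documentation.
3. Report the Phase 2 response rate by the 1996 criteria as a sensitivity analysis. Section 5.3.1.1 already has Phase 2a subjects assessed on both sets. State how the all-items rule treats subjects without abnormal nodes at baseline, since its abnormal-before-therapy qualifier covers only liver and spleen.

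**Cost.** Wording and re-analysis of recorded data, with no new visits. The response rate may fall, some subjects may not be re-derivable, and derived progression may differ from the progression used for treatment decisions. Abnormal at baseline must be defined for each site, because the documents do not define it. The SAP describes completed analyses, so the re-derivation cannot be presented as pre-specified.

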Subjects who meet the criteria above for a CR but exhibit persistent bone marrow lymphoid infiltration will be referred to as nodular PRs (nPR). In addition, subjects who meet the criteria above for a CR but exhibit persistent thrombocytopenia or anemia unrelated to disease activity and attributable to a persistent drug toxicity will be considered PR's.

A summary of the criteria described above is included in [Table 10](#).

Table 10. NCI-WG Criteria for Tumor Response (1996)

Criteria	Complete Remission (CR)	Nodular Partial Remission (nPR)#	Partial Remission (PR)	Progressive Disease (PD)
Symptoms	Absent	Absent	Absent or present	Not specified
Lymphadenopathy	Absent	Absent	≥ 50% reduction	≥ 50% increase* or new nodes
Hepatomegaly and/or Splenomegaly	Absent	Absent	≥ 50% reduction	≥ 50% increase or new hepatomegaly and/or splenomegaly
Neutrophils/ Polymorphonuclear Leukocytes (× 10 ⁹ /L)	≥ 1.5	≥ 1.5	≥ 1.5 or ≥ 50% improvement from baseline	Not specified
Lymphocytes (× 10 ⁹ /L)	< 4	< 4	≥ 50% reduction from baseline	≥ 50% increase with at least 5 × 10 ⁹ /L
Platelets (× 10 ⁹ /L)	> 100	> 100	> 100 or ≥ 50% improvement from baseline	Not specified
Hemoglobin (g/dL) untransfused	> 11	> 11	> 11 or ≥ 50% improvement from baseline	Not specified
Bone Marrow Aspirate/Biopsy	Normocellular < 30% lymphocytes; No intestinal or nodular infiltrates	Normocellular < 30% lymphocytes; Nodular infiltrates	May be normal (i.e., < 30% lymphocytes without interstitial or nodular infiltrates) or persistent disease	Not specified
Other	NA	NA	NA	Transformation to RS or PLL

NA = not applicable; RS = Richter syndrome; PLL = Prolymphocytic Leukemia (with > 55% prolymphocytes); # = nPR is no longer applicable due to the utilization of immunohistochemistry; * = sum of products of at least 2 lymph nodes

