Hemoglobin	> 11 g/dL (untransfused and without erythropoietin)	> 11 g/dL or ≥ 50% improvement from baseline	Decrease of > 2 g/dL from baseline secondary to CLL	Increase < 11 g/dl or < 50% over baseline or decrease < 2 g/dL
Bone Marrow Aspirate/Biopsy	Normocellular, < 30% lymphocytes, no B-lymphoid nodules, Hypocellular marrow defines CRi	≥ 30% lymphocytes, or B-lymphoid nodules, or not done	Increase of lymphocytes to more than 30% from normal	No change in marrow infiltrate

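### Table 11 departs from the 2008 response criteria it summarises on lymphocyte progression, CR marrow and CRi, and no rule says which governs

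*Protocol*

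**What the plan says.** Protocol Section 5.3.3.1.2 defines CR, CRi, PR, PD and SD in text and then introduces Table 11 with the words "A summary of the criteria described above is included in". It gives no rule for cases where the two disagree.

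- **PD by lymphocytes.** Text item 5 asks for a rise of at least 50%, stated as an "increase in the absolute number of blood lymphocytes with at least 5,000 B-lymphocytes per" microlitre. Table 11, in its row for circulating clonal B-lymphocytes, asks for "≥ 50% increase over baseline".
- **CR marrow.** The text wants the marrow shown free of clonal cells and adds that "cases with residual CLL cells by conventional flow cytometry or immunohistochemistry are defined as a PR". Table 11 describes a CR marrow by normal cellularity, under 30% lymphocytes and no B-lymphoid nodules.
- **CRi.** The text means a subject who meets all CR criteria but has persistent anemia, "thrombocytopenia or neutropenia apparently unrelated to CLL, but related to drug toxicity", with no clonal infiltrate in the marrow. Table 11 says "Hypocellular marrow defines CRi".
- **Symptoms (minor).** Table 11, in the column order CR, PR, PD, SD, reads "Constitutional Symptoms Absent Present Present Present". The text sets no symptom condition for PR, SD or PD. Table 10, the 1996 summary, gives "Absent or present" for PR.

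The investigator assesses response (Section 5.3.3.1.2). The SAP applies the 2008 criteria to Phase 2 and bases ORR, best response, disease control rate (DCR), PFS, TTP and duration of response on the resulting categories. Section 5.3.3 of the protocol calls all Phase 2a efficacy analyses exploratory.

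**The concern.** A summary table should give the same answer as the text it condenses. Here, two investigators holding identical data can record different categories, one working from the text and one from the table, and both would be following the protocol. The SAP does not say which version the Phase 2 categories follow and describes no check of them. Preliminary efficacy is a stated Phase 2a objective, and with 31 subjects analysed a single category change shows in the reported rates. A progression call also bears on whether a subject stays on study (Section 5.4.1), which is a further reason to reconcile the passages.

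**Working it through.** The plan has no figure of its own to reproduce: Section 8.2 gives about 32 Phase 2a subjects without a formula, and no calculation uses the response criteria. The check is a comparison of the text with Table 11.

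**1. PD by lymphocytes.** Inputs: a 50% rise (both versions) and a floor of 5,000/µL (text only). I treat the rise and the floor as measured on one B-cell count. The table names baseline as its reference. Text item 5 names none, and Section 8.1.3.5 uses the smallest on-treatment measurement for duration of response.

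- Table rule: current ≥ 1.5 × baseline.
- Text rule: current ≥ 1.5 × reference and current ≥ 5,000.
- A 50% rise can stay below the floor when 1.5 × baseline < 5,000, that is, baseline < 5,000/1.5 = 3,333/µL.

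| Baseline | Nadir | Current | Text, baseline reference | Text, nadir reference | Table 11 |
|---|---|---|---|---|---|
| 2,000 | 2,000 | 3,200 (+60%) | not PD | not PD | PD |
| 3,300 | 3,300 | 4,950 (+50%) | not PD | not PD | PD |
| 3,334 | 3,334 | 5,001 | PD | PD | PD |
| 10,000 | 10,000 | 15,000 | PD | PD | PD |
| 100,000 | 1,000 | 6,000 | not PD | PD | not PD |

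With baseline as the reference, the two versions disagree only below 3,333/µL, and there the table adds progressions. If the text is read against the nadir, they can also disagree the other way (last row). Table 10 keeps the 5 × 10⁹/L floor for the 1996 criteria, so its absence from Table 11 is not a shared shorthand.

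**2. CR marrow.** Take a subject who meets every other CR condition and whose marrow has under 30% lymphocytes, no nodules, and residual CLL cells by flow cytometry. Table 11 gives CR; the text gives PR.

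**3. CRi.** Two cases, both otherwise CR with a clone-free marrow:

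- Drug-related platelets of 80,000/µL with normal cellularity. The text gives CRi. Table 11 gives neither CR (platelets must exceed 100,000/µL) nor CRi (the marrow is not hypocellular).
- Normal blood counts with hypocellular marrow. The text gives CR; Table 11 gives CRi.

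**4. Which endpoints move.** ORR = CR + CRi + PR (Section 8.1.3.2; SAP, Response Rate). Moving one subject from CR to PR gives (CR − 1) + CRi + (PR + 1), the same total, and a CR/CRi exchange behaves likewise. Points 2 and 3 therefore act mainly on the split of best response. Point 1 changes the progression date or status, and so PFS, TTP, duration of response and DCR.

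**5. Size.** One subject is 1/31 = 3.2 percentage points of any Phase 2 rate it affects. For illustration, with assumed counts and exact binomial intervals, 9/31 = 29.0% (95% CI 14.2 to 48.0) and 10/31 = 32.3% (16.7 to 51.4). The documents do not allow a count of subjects affected.

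**6. Can categories be re-derived?** The text rule needs a B-cell count. Table 7 hematology lists lymphocytes without subsets. Under Table 3, scheduled lymphocyte enumeration in Phase 2a is at Screening, C1D15, the end of C4, every third cycle after that (C7, C10, C13, C16) and the Final Visit. Tumor assessments through Cycle 20 are at the end of C2, C4, C8, C12, C16 and C20. The two coincide at C4 and C16 but not at C2, C8, C12 or C20.

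**The case against.** The best defence is that Table 11 calls itself a summary, so the text is naturally the source; that its use at sites in preference to the text is conjecture; and that every efficacy endpoint is exploratory. The SAP is also written in the past tense with 31 subjects already analysed, so editing the table cannot alter how past visits were scored. All of this limits the weight of the point. It does not settle precedence, which no section states, or show which version investigators followed.

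Four stronger readings are tempting, and the documents do not support them:

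- **An asymptomatic partial responder fits no category except CR.** This requires every cell of a column to match. That cannot be how the PD column works, since the text needs only one PD criterion, and the text makes SD the residual class. The symptoms row is a wording fault to tidy up.
- **The marrow and CRi conflicts change ORR.** CR, CRi and PR all count. The subject with platelets of 80,000/µL would normally still qualify as PR, because the text needs only one blood-count condition and neutrophils can supply it.
- **CRi by the text would typically come with a normocellular marrow.** Sections 3.0 and 6.7.2 describe platelet apoptosis rather than myelosuppression, but neither reports marrow cellularity in responders. Subjects may have had up to five prior regimens, and Section 3.0 notes reduced marrow reserve in CLL. How often this case arises is unknown.
- **A table-based PD automatically ends treatment.** Section 5.4.1 frames discontinuation through the investigator's judgment, although the Extension Study text in Section 5.3.1.1 is firmer.

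**Conclusion.** The point holds on three contradictions: the missing B-lymphocyte floor for PD, the missing clonality requirement for CR, and a different definition of CRi. Only the first can alter PFS, TTP, duration of response and DCR. With baseline as the reference and one count used for both rise and floor, it arises only for subjects starting below 3,333/µL. The second leaves ORR unchanged, and the third mainly alters the CR/CRi/PR split. The symptoms row is a minor fourth item. No document shows that any subject had a lymphocyte count in the affected range or a discordant marrow, so a reader should not infer that reported results are wrong, only that the documents do not fix how they were scored. With exploratory endpoints this should be corrected, but it does not threaten a confirmatory conclusion.

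**What to change.** State in Section 5.3.3.1.2 that its text governs endpoint classification, and align Table 11 to it:

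- add the floor of 5,000 B-lymphocytes/µL to the PD lymphocyte cell;
- put the absence of clonal B-CLL cells by flow cytometry or immunohistochemistry in the CR marrow cell;
- let the PR marrow cell allow any result, including not done, because the text sets no marrow condition for PR and a clear marrow with residual nodes must remain PR;
- replace the hypocellular-marrow definition of CRi with the text's drug-related cytopenia and no clonal infiltrate;
- list symptoms as absent or present for PR, SD and PD.

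In the SAP, state that Phase 2 categories follow the text. Check investigator-recorded categories against it wherever the B-cell count and marrow flow or immunohistochemistry results were collected, and report the assessments where they were not.

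The cost is table wording, a short SAP statement and a limited check, with no new assessments. Some recorded categories may change. Others cannot be verified, because scheduled B-cell counts miss several tumor assessments and the documents do not show that marrow clonality was captured as a case report form field.
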